9.6. Patient Replacement Criteria

Patients who withdraw from the trial prematurely will not be replaced. If a substantial number of patients withdraw prematurely, the sponsor will evaluate the need for developing replacement criteria.

Enrolled patients (defined as randomized) who are subsequently withdrawn from the trial may not re-enter. The patient number for a withdrawn patient will not be reassigned to another patient.

10. TREATMENTS

10.1. Identification of Investigational Product

Dasiglucagon Injection, 4 mg/mL will be supplied by the sponsor in a 3 mL vial containing 1 mL of drug product.

Matching placebo for dasiglucagon injection will be supplied by the sponsor in a 3 mL vial containing 1 mL of drug product.

Dasiglucagon and matching placebo will be provided in the form of solution for injection for subcutaneous administration through an infusion pump.

The trial drug product, as applicable, must be transferred from the vial to the Accu-Chek Spirit Cartridge. The amount of drug product dosed via the pump will vary among patients.

Cartridges and infusion sets should be filled and replaced as indicated in the instructions for use.

10.1.1. Packaging and Labeling

Trial drug products will be packaged and labeled by the sponsor.

Part 1 dispensing unit configuration: 3 vials containing dasiglucagon, 4 mg/mL or placebo for dasiglucagon, packed in an outer carton. The vials and carton will be packaged and labeled in local language without revealing the treatment.

Part 2 dispensing unit configuration: 3 vials containing dasiglucagon, 4 mg/mL, packed in an outer carton. The vials and carton will be packaged and labeled in local language, revealing the treatment.

The storage conditions for trial drug products will be described on the trial drug product label. The labels will supply no information about patients. Each dispensing unit (3 vials) will have a unique Dispensing Unit Number for drug allocation, drug accountability, and traceability purposes.

Labelling will be performed according to Annex 13 of the Good Manufacturing Practice guidelines of the European Commission, ICH Good Clinical Practice (GCP) guidelines, local laws, and regulations.

10.2. Treatments Administered

As long as the patient is receiving IV glucose, the PG will be measured and reviewed hourly using a hand-held PG meter. The IV GIR will be titrated to achieve glycemia of at least 70 mg/dL (3.9 mmol/L) (a minimum GIR will be established as the rate up-titrated after the patient drops at least once below 70 mg/dL [3.9 mmol/L]). When the patient is no longer on IV GIR, the PG will be checked according to local practice, but at least 3 times daily. The PG will be measured using the same trial-supplied hand-held PG meter during the entire trial.

Additionally, blinded CGM will be started 24 hours prior to randomization and continued until the end of Part 2.

Dosing of dasiglucagon will approximate continuous infusion by delivering small doses at frequent intervals via the infusion pump. The adjustment of trial drug dosing is closely linked to the PG level achieved, which in turn will govern the IV GIR. In Part 1 the algorithm in [Table 1](#) should be used.

The pump administers 0.000025 mL/dose ~ 0.1 µg/dose (4 mg/mL formulation):

- 10 µg/hr ~ 0.5 µg every 3 min
- 20 µg/hr ~ 1 µg every 3 min
- 30 µg/hr ~ 1.5 µg every 3 min
- 40 µg/hr ~ 2 µg every 3 min
- 50 µg/hr ~ 2.5 µg every 3 min
- 60 µg/hr ~ 3 µg every 3 min
- 70 µg/hr ~ 3.5 µg every 3 min

Table 1 Algorithm to Maintain Plasma Glucose

Plasma Glucose (mg/dL)	Plasma Glucose (mmol/L)	Action
<50	<2.8	Give 200 mg/kg of dextrose as a bolus and increase IV GIR by 2 mg/kg/min
50-59	2.8-3.3	Increase IV GIR by 2 mg/kg/min
60-69	3.3-3.9	Increase IV GIR by 1 mg/kg/min
70-80	3.9-4.4	No change
81-90	4.4-5.0	Reduce IV GIR by 0.5 mg/kg/min
91-100	5.0-5.5	Reduce IV GIR by 1 mg/kg/min
101-120	5.5-6.7	Reduce IV GIR by 1.5 mg/kg/min
>120	>6.7	Reduce IV GIR by 2 mg/kg/min

Abbreviations: GIR = glucose infusion rate; IV = intravenous

The IV GIR will be reviewed, evaluated, and adjusted (if indicated) every hour according to the above PG-driven algorithm to maintain a PG of >70 mg/dL (>3.9 mmol/L). Rechecks of PG are allowed.

Part 1 (Crossover, double-blind, randomized, placebo-controlled)

The starting dose of trial drug is 10 µg/hr at t=0. Every 2 hours (t=2, 4, 6, etc.), the dose will be increased by an additional 10 µg/hr until either:

- The patient is totally weaned off IV glucose, or
- Plasma glucose during the last 2 hours was constantly above 120 mg/dL (6.7 mmol/L), or
- IV GIR has not decreased despite 2 sequential dose increments of trial drug (in this situation, the dose of trial drug should be maintained until the IV GIR can be further decreased or until crossover or the end of Part 1), or
- The maximum dose of 70 µg/hr is reached, or
- AEs emerge that are considered to be related to dasiglucagon (e.g., nausea/change in feeding pattern or increased vomiting) that are limiting further dose escalation

The 2-hour dose-adjustment interval will allow drug plasma levels to approach steady-state before the dose is further increased. The cumulative dose will not exceed 1.26 mg over the first 24 hours and 1.68 mg for each of the subsequent 24-hour periods.

At the time of crossover from the first 48-hour period to the second 48-hour period, the trial drug will again be titrated from the starting dose of 10 µg/hr, and IV GIR will be set to the rate obtained at the end of the run-in period and titrated accordingly.

Part 2 (Open label)

After Part 1, patients will continue in open-label Part 2 to receive dasiglucagon for a further 21 days. Since treatment allocation during Part 1 remains blinded, all patients are required to initiate dasiglucagon dosing at 10 µg/hr in Part 2, while IV GIR should be started at the rate obtained at the end of the run-in period.

During Part 2, the dasiglucagon dose, the amount and route of administration of carbohydrates (IV GIR, parenteral nutrition, gastric carbohydrate infusions, and carbohydrates from oral feeds) can be adjusted at the discretion of the investigator. The PG should be monitored at least hourly to adjust the IV GIR as appropriate and to avoid hypoglycemia. Additional concomitant medications, including somatostatin analogs and/or sirolimus/mTOR inhibitors, may be introduced at the investigator's discretion if the maximum dose level of dasiglucagon (70 µg/hr) has been reached or if further up-titration is not possible due to undesirable side effects.

Adjustment of total carbohydrate administered (IV glucose, parenteral nutrition, carbohydrate infusions, and carbohydrates from oral feeds) should continue throughout this period according to local practice to maintain PG levels in the range of 70 mg/dL to 120 mg/dL (3.9-6.7 mmol/L). The aim will be to obtain stable glucose levels with minimum rescue/hypoglycemia-preventative carbohydrates administered by invasive routes, and to encourage/optimize oral feeds, and achieve weaning off IV glucose. Regardless of their discharge status, all patients will be offered the opportunity to participate in the long-term safety extension trial (ZP4207-17106), providing the investigator attests to the positive benefit-risk balance of continued dasiglucagon treatment.

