9.2.3. Randomization Exclusion Criteria

A screened patient will not be randomized if:

1. Mean IV glucose requirement is <10 mg/kg/min to maintain glycemia above 70 mg/dL (3.9 mmol/L) during the previous 24 hours prior to randomization
2. Use of glucagon within 24 hours before randomization.
3. Use of additional enteral glucose within 24 hours before randomization. Patients should be transitioned to IV glucose infusions only at least 24 hours before randomization.
4. Is not sufficiently clinically stable on IV GIR only (\pm diazoxide, as applicable), in the opinion of the investigator, to undergo the placebo-controlled randomized Part 1 of the trial (2x48 hours).

The Randomization Visit may be rescheduled once if Randomization Exclusion Criterion 2 is met.

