11.2. Assessments

11.2.1. Efficacy

11.2.1.1. Plasma Glucose Monitoring

As long as the patient is receiving IV glucose, the GIR will be reviewed hourly, based on an hourly PG check performed by the StatStrip Xpress2 meter. The IV GIR will be reviewed, evaluated, and adjusted (if indicated) according to the IV GIR algorithm based on PG levels specified in Table 1. If IV glucose has been stopped, PG will be checked according to local practice, but at least 3 times daily.

Blood for PG check can be obtained either by finger or heel sticks or by an indwelling peripheral line. However, if using an indwelling peripheral line, the total blood volume drawn during a 28-day period should be considered according to Section 11.2.3.1.

At each visit, the investigator will ensure that SMPG data are downloaded from the patient's device. The investigator will check for patient compliance in SMPG measurements. The procedure for download of SMPG data will be described in the pharmacy manual/TMM.

Adjustments to the trial drug will be made as outlined in Section 10.2.

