13.2. Sample Size Determination

A total of 12 patients is planned to be randomized and exposed to trial product in this crossover trial on the basis of the following considerations.

The GIR results from 40 infants treated with IV glucagon for 24 hours published in the JIMD Research Report “The Effect of Continuous Intravenous Glucagon on Glucose Requirements in Infants with Congenital Hyperinsulinism.”¹⁴

“Overall there was a statistically significant reduction in the median (IQR) GIR during the 24h following initiation of continuous glucagon infusion compared to 24 h before initiation (18.5 (12.9, 22.8) to 11 (6.6, 17.5) mg/kg/min...”

This trial is powered to detect an effect in GIR for dasiglucagon after 48 hours compared to placebo of at least this effect size. Based on the longer infusion and titration of dasiglucagon in this trial, this is considered a conservative approach, allowing for some uncertainty when translating the published data into a clinical trial setting. Using unpublished individual patient data from the above-referenced study, the difference in GIR between the 2 treatment groups is assumed to follow a normal distribution. Assuming the true mean difference is 7.5 mg/kg/min with a standard deviation of differences of 7.36, the trial will have 89% power using a 1-sample t-test with 12 patients randomized to receive either placebo first and then dasiglucagon or vice versa.

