20.2.1.2. Self-Monitoring Plasma Glucose StatStrip Xpress2

To assess plasma glucose levels and events of hypoglycemia, SMPG measurements will be taken. The plasma glucose level will be assessed at least 3 times daily and in cases of suspected hypoglycemia throughout the trial.

The hand-held StatStrip Xpress2 meter GLU/KET from Nova Biomedical is to be used to measure glucose and ketone levels in the design of the trial. The ketone measurement will only be performed by trial staff when the patient is in the clinic.

The SMPG meter manufactured by Nova Biomedical is a small (size of 98.0 × 64.0 × 22.9 mm and a weight of 78.5 g) battery-powered meter. Blood sample strips are inserted and glucose (in mg/dl or mmol/L) and ketone values (in mmol/l) will be displayed on the screen. Function and data selection are done by choosing 1 of 3 buttons. Up to 400 measurements can be stored in the device memory.

The test strip is designed with an electrode that measures glucose levels. Glucose in the blood sample mixes with reagent on the test strip, which produces an electric current. The amount of current that is produced depends on the amount of glucose in the blood. The electrical current is detected by the monitor and displayed as the glucose value. The test strip is designed such that when a drop of blood touches the end of the strip, the blood is drawn into the reaction space via capillary action. Test strips are available in cartons of 100 strips: 50 strips/vial. Additionally a QC control glucose/ketone solution is provided to test device functionality.

The manufacturer Nova Biomedical Corporation, [name] (European Authorized Representative Nova Biomedical U.K.; [name]) have self-declared conformity with the EU Directive 98/79/EC In Vitro Diagnostic Medical Device Directive. This SMPG device is marketed as an In Vitro Diagnostic Device. The SMPG device is intended for in-vitro diagnostic use by health care professionals and for point-of-care usage in the quantitative measurement of glucose in fresh capillary, venous, arterial, and neonate whole blood; it can also be used for quantitative determination of beta-hydroxybutyrate-ketone in fresh capillary and venous blood samples. It is not intended for diagnosing or screening for diabetes.

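### In Part 1 the hourly glucose check lapses once IV glucose stops, so a weaned infant may have only three required checks a day; separately, the SAP's linear trapezoid does not fit a stepped infusion rate

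*Protocol*

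**What the plan says.** The monitoring rule has two tiers. Protocol 11.2.1.1 sets the first: "As long as the patient is receiving IV glucose, the GIR will be reviewed hourly, based on an hourly PG check". The second follows: "If IV glucose has been stopped, PG will be checked according to local practice, but at least 3 times daily". Section 10.2 says the same ("When the patient is no longer on IV GIR, the PG will be checked according to local practice, but at least 3 times daily"), versions 13.0 and 14.0 agree, and SAP 3.4 repeats it. None of these places limits the lower tier to Part 2.

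The sentence below Table 1 is worded more broadly: "The IV GIR will be reviewed, evaluated, and adjusted (if indicated) every hour according to the above PG-driven algorithm". The schedule of events, however, shows IV GIR adjustment as continuous only until the infant is weaned. The other hourly-monitoring sentence in 10.2 stands under Part 2 and concerns adjusting the IV GIR.

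Total weaning is a foreseen Part 1 outcome. The first condition that ends up-titration in 10.2 is "The patient is totally weaned off IV glucose". In its definition of time to complete weaning, SAP 6.1.7 accepts that some weaned patients may later need IV glucose again. Neither document gives a Part 1 rule for restarting from zero.

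CGM is blinded in both parts (11.2.1.2), and the German addendum says that the G6 gives no alarm (20.2.1.3). That addendum also states: "The plasma glucose level will be assessed at least 3 times daily and in cases of suspected hypoglycemia throughout the trial". Version 13.0 has no matching line for Part 1.

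For the primary endpoint, SAP 6.1.7 computes the area under the GIR curve by the linear trapezoidal method and divides by the length of the period. Protocol 13.4.3.1 asks for a time-weighted mean and does not name the trapezoid.

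**The concern.** These infants have severe disease. Protocol 9.2.3 bars randomization if "Mean IV glucose requirement is <10 mg/kg/min to maintain glycemia above 70 mg/dL" over the preceding 24 hours. Once weaned on dasiglucagon, such an infant depends on a subcutaneous pump delivering a drug with a half-life of roughly 22 to 30 minutes (8.1), and the German addendum lists infusion set blockage as a possible cause of glycemic events (20.3.2). Scheduled dose increases and the requirement for hourly checks end at the same moment. If need returns, nothing in the protocol requires anyone to look until the next check.

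There is a smaller consequence for the endpoint. Last-12-hour GIR stands for glucose requirement because an hourly algorithm drives it. While the infant is off IV glucose and checked less often, a recorded rate of zero may reflect no need or need that nobody measured. Given the entry requirement, zero GIR is likelier on dasiglucagon, so missed need would tend to enlarge the apparent effect.

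The trapezoid is a separate matter. An infusion rate holds until someone changes it. A straight line between two recorded rates credits glucose that was not infused when the rate rises and omits glucose that was infused when it falls, unless the values in between are logged. The documents do not say whether a zero rate is logged between stop and restart.

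**Working it through.** **The plan's own figure.** Mean difference 7.5, SD of differences 7.36, n = 12, two-sided 0.05 (Protocol 13.2 and 13.4). Noncentrality = 7.5 / (7.36/√12) = 3.53; the one-sample t-test on 11 df has power 0.894. The stated 89% reproduces and is not in dispute.

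**Can zero GIR occur before hour 36?** Yes. From 10 mg/kg/min, Table 1's largest reduction (2 per hour) reaches zero in 10/2 = 5 hours and its smallest (0.5 per hour) in 10/0.5 = 20 hours.

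**Required gap.** 24/3 = 8 hours if the three checks are evenly spaced. The spacing is not stated.

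**Illustration of the endpoint effect.** All inputs here are assumptions. The infant is off IV glucose at the start of the 12-hour window. Need N (1, 2 or 4 mg/kg/min) returns just after a check. With hourly checks, GIR restarts at 1 hour and rises by 2 per hour to N. At the floor, it restarts at 8 hours directly at N. Means over 12 hours:

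| N | Hourly, step | 8-h gap, step (4N/12) | Shortfall, step | Shortfall, trapezoid |
|---|---|---|---|---|
| 1 | 0.92 | 0.33 | 0.58 | 0.29 |
| 2 | 1.83 | 0.67 | 1.17 | 0.58 |
| 4 | 3.50 | 1.33 | 2.17 | 1.00 |

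For N = 4, the hourly step mean is (1×2 + 10×4)/12 = 3.50. The trapezoid column assumes that only the stop and the restart changes are logged. The 8-hour gap then gives (8N/2 + 4N)/12 = 2.67 at N = 4, against 3.67 with hourly checks.

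The shift in the 12-patient mean difference is the shortfall × k/12 for k affected infants. For k = 1 to 3:

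- step: 0.58×1/12 = 0.05 to 2.17×3/12 = 0.54 (7.2% of 7.5);
- trapezoid: 0.29×1/12 = 0.02 to 1.00×3/12 = 0.25 (3.3%).

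**Need returning at a random time in the gap.** Average delay is 4 hours at the floor and 0.5 hour with hourly checks. For N = 4 with the same ramp, the hourly mean is (7.5×4 - 2)/12 = 2.33, and the shortfall is 2.33 - 1.33 = 1.00 per infant. With three infants that is 0.25 (3.3%). Under the trapezoid, the gap is credited 8N/12, which equals the average true need of (12 - 4)N/12, so against true need the shortfall is about 0.

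If the late restart also climbed by 2 per hour, the N = 4 step shortfall would grow by 2/12 = 0.17 per infant, or 0.04 on the mean difference with three infants.

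**Against the significance threshold.** The smallest significant difference at the planned SD is 2.201 × 7.36/√12 = 4.68. An observed 7.5 less 0.54 is 6.96.

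**Trapezoid error alone.** In the 8-hour example the trapezoid gives 8N/12 where 4N/12 was infused, an excess of N/3: 0.33, 0.67 and 1.33 mg/kg/min for that infant.

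**Burden of hourly checks in hours 36-48.** 12 checks against 12×3/24 = 1.5 at the floor, so 10.5 more per period.

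**The case against.** The working rule is local practice, and three a day is only the backstop. Part 1 patients are inpatients at sites experienced in CHI (8.3), rechecks are allowed, and the broadly worded sentence below Table 1 can be read as continuing hourly review. Table 1 lowers GIR only at readings of 81 mg/dL or more, so an infant reaches zero from a safe value. Weaning stops dose increases, not the drug. IV glucose may be raised to avoid hypoglycemia (9.5), and once a low is found further glucose values are recorded (11.2.3.3). At crossover GIR returns to the run-in rate, and hourly checks resume with it.

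Much of this stands. It makes an 8-hour gap a possibility under the rule, not something the documents show to happen. It does not close the gap before detection: 9.5 and 11.2.3.3 act only once a low is found or suspected, and 11.2.1.1 and the schedule both tie hourly review to running IV glucose.

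The objection is strongest against the endpoint. A reader might infer that the treatment effect is materially inflated. That would need weaning, a rebound inside the window, checks no denser than the floor and no clinical detection, all together, and the documents establish none of these. A reader might also take the planning data ("compared to 24 h before initiation (18.5 (12.9, 22.8) to 11 (6.6, 17.5) mg/kg/min") to show that about a quarter of infants would be affected. Its lower quartile of 6.6 on IV glucagon, a different product and route, says nothing about reaching zero or rebounding.

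**Conclusion.** The gap in the Part 1 monitoring rule is real, appears in both protocol versions, and matters mainly for safety. How long returning hypoglycemia could go unseen depends on local check frequency, which the documents do not report.

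The effect on last-12-hour GIR is conditional and small, and would tend to favour dasiglucagon. The documents do not fix its size. The illustration gives 0 to about 0.5 mg/kg/min on a difference of 7.5 at the extreme, and at most about 0.25 with a random return time; N, the number affected and the 8-hour gap are all assumed. It is zero if no infant is weaned, if zero is the true need, or if sites keep checking hourly. Nor do the documents support reading this as a threat to the significance test: 6.96 stays above 4.68, though that comparison holds only for an observed difference of 7.5 at the planned SD.

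The trapezoid point does not depend on any rebound. It applies wherever the rate changes and the values in between are not logged.

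**What to change.** 1. **Protocol 10.2 and 11.2.1.1, versions 13.0 and 14.0.** State that in Part 1 hourly glucose checks and Table 1 review, including restart from zero, continue at least through hours 36-48 of each period whether or not IV glucose is running. Cost: one sentence per section and, for a weaned infant, about 10-11 extra capillary checks per period compared with the floor, in patients as small as 2 kg. Where local practice is already denser, the added burden is less. It cannot help patients already through Part 1, and SAP 8.1 shows that crossover data were already in the database.

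2. **SAP 6.1.7, before unblinding.** Calculate the weighted mean IV GIR as a step function between recorded rate changes, with zero from stop to restart. Cost: one sentence. It fits the time-weighted mean in Protocol 13.4.3.1 and also serves patients who have finished Part 1.

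3. **Optional.** Add one descriptive by-treatment table for the last-12-hour windows: number of glucose checks, hours at GIR 0, and low glucose while GIR is 0. The glucose efficacy endpoints are planned for Part 2 only (SAP 2.2.2), so no planned efficacy table shows this. The data are already collected. If CGM is used, footnote the off-label age group and the paracetamol interference with the G4.

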10.3. Trial Supplies

The device and ancillaries listed in the following table will be supplied by the sponsor throughout the trial. Trained trial personnel will train parent(s)/guardian on the use of the devices. Instructions for the use of all these supplies will be provided in separate manuals.

Item	Name	Manufacturer
Pump	Accu-Chek Spirit Combo	Hoffman-La Roche AG, Basel, Switzerland
Cartridge	Accu-Chek Spirit 3.15 mL Cartridge system	Hoffman-La Roche AG, Basel, Switzerland
Infusion sets	Accu-Chek FlexLink Infusion set (Accu-Check UltraFlex Infusion set in US) and Accu-Chek Rapid-D Link Infusion set	Hoffman-La Roche AG, Basel, Switzerland
Infusion set inserter	Accu-Chek LinkAssist Insertion device (can be used with FlexLink & UltraFlex)	Hoffman-La Roche AG, Basel, Switzerland
SMPG	StatStrip Xpress2	Nova Biomedical, Waltham, MA, USA
CGM	Dexcom G4 (not to be used in Germany) Dexcom G6	Dexcom Inc., San Diego, CA, USA

The infusion pump system is CE-marked for the management of diabetes mellitus in persons requiring insulin, as prescribed by a physician. In this trial, the pump system is used outside of the CE-marked intended use since the pump system will be delivering dasiglucagon to patients with CHI. The PG meter is used as intended according to the CE mark, except for the use by a lay person in a home care setting. The CGM devices are used as intended according to the CE mark, except for the age group and the disease.

The pump, the SMPG, and the CGM will be labeled for use in an investigational trial. For more information on the devices please refer to Section 20.

